Social and Behavioral Intervention to increase solid organ and tissue donation

Clinical Trials Number: NCT02318849

[figure not shown]
Unique protocol number: R39OT26993 from the Health Resources and Services Administration

Document date: May 27, 2023

Study Design/Intervention Protocols and Statistical Analyses Protocols

The eHealth study used a cross-sectional design that included a sequential, multiple baseline survey design that was introduced over two years at the three Hawaii university campuses. For example, undergraduate students at one site (University of Hawaii at Manoa-UHM) participated in three semesters of the DOD intervention and students at two sites (University of Hawaii at Hilo-UHH), Hawaii Pacific University-HPU) received two sequential semesters. **Figure 1** shows the study design with pre/post surveys and a sequential introduction of the intervention across three years (four semesters).

Figure 1. Study Design

Thus, either a baseline or post-test survey was administered at the start and/or the end of a semester depending on when the online intervention was introduced at a site. All students at the site were recruited to take the surveys regardless of whether or not they had completed a survey at any point in the past. Therefore, some survey analyses included cross-sectional samples and some analyses included a cohort sample of students. Data collection protocols for online surveys from undergraduate students were approved by the University of Hawaii's Human Studies Program in October 2014 (CHS 22372) with Hawaii Pacific University's Institutional Review Board ceding to the University of Hawaii's IRB.

Survey questions for primary outcomes:

[figure not shown]
- 1. Status as a designated organ donor on Department of Motor Vehicles (DMV) issued driver's license, state-issued ID card or donor registry.
- 2. Reported discussion about their choice to be (or not be) an organ donor on their DMV issued driver's license with their parents or other family members.

Protocol for Sample Size / **Power calculations for surveys:** Simulations were run to determine the achieved power of our multiple baseline design resulting in an average of 240 participants per site for surveys collected at the beginning and end of four academic semesters at UHM and UHH and five academic semesters for HPU (20 data points, total n = 4,800). We assigned 60% of the students at baseline to already be a DOD (prior to being exposed to the intervention), based on the proportion we observed in previous work. Using an α =0.05 (two-sided) and a power of 80%, a simulation of 500 iterations found that the minimum detectable difference (MDD) in DOD prevalences comparing the 9 pre- and 11 post- intervention assessments, using our analysis approach, was 4 percentage points for an average change overall (3 campuses) and was 7 percentage points within a single campus; this was true assuming no change or a 3 percentage point drift in the pre-intervention prevalences over time.

Protocol for recruiting students for Study Surveys and Intervention activities Before taking the iDecide survey, students had to confirm they had read the consent form and actively consent (click yes). Eligibility was the verified. Only undergraduates enrolled at the three participating universities (UHM, UHH, HPU) were eligible, with enrollment verified by the respective university. Age was the only other eligibility criteria (18 years or older). Of the 8,001 online

consent forms completed, 853 (10.7%) reported enrollment at a nonparticipating university, and 2,073 (25.9%) didn't finish the survey. After verifying enrollment status for the remaining 5,075 survey entries, 248 (4.9%) were excluded because the student was not currently enrolled or was a graduate student, or their survey was a duplicate within that assessment; 4,837 was the final count.

Between November 2014 and December, 2016, undergraduate students were independently recruited to complete surveys (compensated for their time with a \$10 Amazon gift code) and to participate in the social media contests during the intervention. That is, students who completed a survey were not informed by project staff about the contests, and students who entered a contest were not recruited by staff to complete a survey. The most commonly used method for recruitment was email with 14,868 emails sent to recruit for the surveys and 41,562 emails to recruit for contests. These emails were sent to faculty at the sites (asking them to inform students about survey), Registered Independent (student) Organizations (RIOs), survey respondents (if student agreed to receive future recruitment notices about surveys offered later in the semester). Previous contest entrants were emailed about remaining contests in that semester. Both print and online advertisements for the various different contests and different ads were used to recruit for the surveys resulting in 467 print ads for surveys and 1,254 print ads for the contests. The ads were placed in campus newspapers, on napkin holders on cafeteria tables in dorms, and on bulletin boards around campuses. Two social media posts for the survey and 282 posts for the contests were designed. They included posts for the contests on the project's homepage /website, and on the project's social media accounts/pages on Instagram and Facebook and on our YouTube channel. Students were also recruited in person via classroom presentations or tables set up periodically at campus centers at each university. Finally, students were recruited for the survey via departmental research websites that gave extra credit to students who participated in research studies. Figure 2 is the Consort Figure for recruitment protocols used for the surveys and contests across all sites/ years and survey accrual results.

Leaders/officers from RIOs on each campus were recruited to serve on the project's Student Advisory Board (SAB) each semester, resulting in a total of 40 RIOs participating. The SAB held up to 4 monthly teleconferences per semester where they provided input on recruitment for surveys and contests plus were informed about current and upcoming contests (for which only RIOs were eligible). At the end of a semester, RIOs that participated in the SAB received \$100.

eHealth Intervention's Study Protocols: The protocols for staff who delivered intervention content were focused on the project's website and social media sites.

Protocols for implementing the intervention: The University of Hawaii at Manoa core research team who designed the project's website (and collected /wrote all the deceased organ donation educational content for it) also designed and conducted the social media based intervention and included the principal investigator, project supervisor, and a Graduate Research Assistant (GRA). A private website developer (Hedges Creative Company in San Diego) was contracted to develop and maintain the project website, its logo, with considerable input from the team and usability/navigation testing done by UH Manoa team. The Hedges Creative Company also took the surveys we designed and our consent form and programmed them into a separate website. After the website was developed and the social media pages created, the UHM team began to recruit students to take the online baseline surveys and enter contests on the study website via presentations in class, booths at the sites' campus centers, posts on social media, print fliers on each campus, and weekly emails to student organizations and to faculty at all 3 sites. We also had two faculty members from the different sites (one from UH Hilo and one from HPU) who helped recruit students to participate in the contests and surveys. Students were involved as well: an unpaid student intern and 40 members of a Student Advisory Board (SAB) across all sites and all semesters. The student intern helped keep students engaged in the contests and informed them about surveys via campus fliers and provided continued awareness about the project during the summer months when the contests were not being held via posts on social media. The SAB consisted of RIOs at each site where at least one member from each organization attended monthly teleconferences to strategize and recruit their peers/members to enter contests and/or take a survey. The number of members on the SAB ranged from 2-4 per semester per site. In summary, there were 46 people involved in implementing the intervention throughout the study from Fall 2014 until the end of Fall 2016.

Training protocols for intervention personnel: All staff on the core research team took IRB required online CITI training modules on Human Subjects Research. The Project Supervisor and GRA were both trained in OD issues by reading articles about deceased organ donation process, using the donor.gov website, and reading research articles written about educating adolescents and college students about the choice to be a DOD on their "adult ≥ 21 driver's license. In addition, the research team was trained by [name] during a consultant meeting on how he had conducted pledge contests with college students/student organizations to increase student engagement in DOD.

Recruitment protocols for study participants to complete surveys and/or enter study contests

The intervention's was designed as open-access; thus, anyone with internet access could read its OD related information and view winning contest entrees. However, only undergraduates currently enrolled at a participating university, during periods when the intervention was active, were eligible to enter a contest. Entrants to all contests agreed to follow contests' rules and regulations (clicked agree), entered their age (only \geq 18 y/o eligible), selected university they were attending, and provided their university email.

Between January 2015 and December 2016, undergraduate students were recruited to enter social media contests during the active intervention periods at their site (see Figure 2). The primary recruitment method was email (n = 41,562 across all contests/all years). Emails were sent to faculty at the sites (to inform students about contests), registered student organizations, and previous contests entrants. Both print and online advertisements (n= 1,254) were created for contests and appeared in campus newspapers, napkin holders on cafeteria tables, and printed flyers on bulletin boards around the campuses. Also, 282 posts were designed by intervention staff and posted on the project's website and social media accounts (i.e., Instagram, Facebook, YouTube). Students were also recruited in person via classroom presentations or tables set up periodically at campus centers of active intervention sites.

Design Protocols of eHealth Intervention website: The home page of the website was designed with three main "links" related to Stage of Change and how users felt about organ donation or their reason for coming to the site. For example, the link "I'm uncomfortable" provided information for those who were Precontemplators or might be disgusted

by the thought of OD, while the "I'm interested, need resources" or "I want to win" links provided information for those in the action stage and came to the site for resources or to register for a contest. See Figure 3 on next page:

Figure 3. Website home page

Protocol for Social Media Contests

Along with the iDecide Hawaii website, project accounts / pages on various social media sites including Facebook, Instagram, and a YouTube channel were created. Facebook and Instagram pages were used to announce the contests, and these platforms, along with YouTube, were used to post the winning entries. Links to our social media pages were located atop each page of the project website. RIOs/SAB members were asked to "like" or "follow" our pages and "share" our posts, so they would be seen by their club members. In order to maximize our social media presence, students were asked to post their picture/video entries on their personal accounts and include our project hashtag (e.g., #idecidehawaiiphoto). This allowed their "followers" to see the video/picture and to be connected to others' entries from the current and previous contests by simply clicking the hashtag.

Protocols included total of 15 to 22 contests per site per semester were held during the intervention, with the largest number of contests (n=58) being held in the Spring of 2016 when all three sites were active in the intervention (see Figure 1). As an indicator of the dose for our gamification protocol, up to seven Instagram picture contests and six Instagram caption contests were held per semester, and five YouTube/Instagram video contests. Additionally, an essay (first person "reporter" story) contest and a pledge contest (members and any currently enrolled student could pledge on behalf of a specific RIO to become a DOD on next license renewal). In addition, two random drawings were held: one in the first week of classes at a campus center table, and another at the end of a semester for contest entrants who entered but did not win a contest. Finally, a referral program was created where those who won a contest more than two times in one semester (and, thus, were no longer eligible to enter that semester) could win a prize by referring another student to enter a contest if that student subsequently won. There were nine themes for the Instagram picture/caption contests, and five themes for Instagram/YouTube (15-60 seconds) video contests.

Table 1 (see next page) lists the specific intervention protocols / themes for each contest on a social media site.

Table1: Organ donation related themes for Social Media contests			
Theme	Instagram picture contest	Instagram Caption contest	YouTube video contest
Hug a Heart!	Sp2015 Fa2015 Sp2016 Fa2016	Sp2015 Fa2015 Sp2016 Fa2016	
Go green recycle yourself!	Sp2016	Sp2016	Sp2015 Fa2015 Fa2016
Be a SUPER HERO! Organ donors can save 8-20 people	Sp2015 Fa2015 Fa2016	Sp2015 Fa2015 Fa2016	Sp2015 Sp2016
What are the odds? You're more likely to need an organ transplant than to be a donor when you die	Sp2015 Sp2016	Sp2015 Sp2016	Sp2015 Fa2015 Fa2016
Bust a myth! Find a myth about organ donation and expose the truth	Sp2015 Fa2015 Fa2016	Sp2015 Fa2015 Fa2016	Sp2015 Sp2016
Not as many as you think! Only 20% of Hawaii college students are designated organ donors	Sp2015 Fa2015 Fa2016	Sp2015 Fa2015 Fa2016	
I'm gonna tell MOM! Talk to your mom (and other family) about your wishes to be a donor	Sp2015 Fa2015 Sp2016 Fa2016	Sp2015 Fa2015 Sp2016 Fa2016	Sp2015
This is what a donor looks like	Sp2015		
I'll do it if YOU do it first! Be an advocate, tell someone you know THEY can save 8 lives and improve the quality for up to 20 more, just by being an organ donor. Spread the word!	Sp2016	Sp2016	

4) Statistical Analyses Protocols

Two types of data sets would be created: a cross-sectional set and a longitudinal set. The cross-sectional dataset would include data from all surveys at each of the 20 assessment points (see Figure 1). The design allowed for students

to complete surveys at more than one assessment point. Due to uniqueness of student email addresses, those with repeat surveys could be identified. Thus, students could complete one or more pre-intervention surveys, one or more post-intervention surveys, or complete both pre and post-intervention surveys. The longitudinal dataset would include only those students who completed one or more baseline surveys and one or more post-test surveys.

The primary hypothesis was that exposure to the intervention would increase the percentage of students who reported being DODs on license and/or who spoke to their parents about their choice to be (or not be) a DOD on their license, and exposure would also improve knowledge and attitudes about OD. The primary analysis of the cross-sectional data used a logistic model of the outcomes DOD status or "talk to parents" regressed on a set of indicator variables reflecting each of the 20 assessment points (time by school combinations), adjusted for student's age, sex, race, and religion. Predicted DOD status (or family talk status) was computed from the model for each assessment point and the predicted statuses were compared between pre-intervention and post-intervention assessments using a t-test to test the primary hypothesis. We also repeated the test within subgroups defined by school and by covariates, such as race, to determine if the intervention effect differed by subgroups. Linear models regressing knowledge and attitude scores on assessment indicator variables and adjustment factors were used to determine the intervention effect on these scores.

The primary analysis models were repeated in the longitudinal sample, accounting for repeated measures. Further, a logistic model of post-intervention DOD status was performed among the longitudinal sample where the students never reported being a DOD at any pre-intervention assessment. All post repeated measures for these individuals were included in one model (allowing for repeated yes answers) and all post repeated measures up until when the first yes reported for DOD was included in a second model. The independent variables included the assessment indicators, age, sex, ethnicity and religion. The predicted percentage adopting DOD would be obtained from the model and tested against 0 using a t-test. This comparison was repeated for each post-intervention time (e.g., 1st post-test) and for each school, as well as by subgroups defined by covariates. A similar analysis was performed for the "talk to parents" outcome in the subset who never reported having this conversation on any pre-intervention survey.

Lastly, in order to determine if the intervention was more effective in students less likely to be a donor, protocols stratified the statistical analyses using a "propensity score" based on static student characteristics. We anticipated that students with characteristics making them less likely to become a DOD might be more influenced by our intervention. Propensity scores were developed for DOD status by using a logistic regression of DOD status using pre-intervention data to determine predictors from among demographic/sociocultural variables (e.g., age, sex, race, religion, place of birth, years lived in HI, college year, tuition source, college major, college credits, recruitment method, study site and time). The resulting DOD model based on 2129 surveys (Donor: Yes=1137, No=992) included significant factors of age, sex, race, college year, religion, and tuition source, using stepwise variable selection. The resulting logistic regression equation would then be applied to all surveys to obtain predicted probabilities that were used as "propensity scores." The primary analyses for the cross-sectional data set was performed separately for surveys with a low propensity score < 50% and for surveys with a high propensity score ≥ 50%. The analyses for the longitudinal data set were also stratified by low and high pre-intervention propensity scores, based on the average for students who provided ≥ 1 pre-test survey.

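### Students may take the survey repeatedly and no analysis uses their survey history, so any effect of the survey itself would not be separated from the intervention effect

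*Combined protocol and SAP*

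**What the plan says.** The opening design section of the combined protocol and SAP states that all students at a site were "recruited to take the surveys regardless of whether or not they had completed a survey at any point in the past". The survey recruitment section adds that recruitment emails went to "survey respondents (if student agreed to receive future recruitment notices about surveys offered later in the semester". The same section excludes an entry if "their survey was a duplicate within that assessment"; a second survey by the same student at a different assessment is kept.

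Section 4, Statistical Analyses Protocols, confirms that the design allowed students "to complete surveys at more than one assessment point" and that "Due to uniqueness of student email addresses, those with repeat surveys could be identified". The use described for this identification is to build the second dataset: "The longitudinal dataset would include only those students who completed one or more baseline surveys and one or more post-test surveys".

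The primary logistic model contains 20 assessment indicators ("time by school combinations), adjusted for student's age, sex, race, and religion"). Its predictions are then compared between pre and post assessments by t-test. The longitudinal rerun adds handling of repeated measures. The adoption models, in students who reported no donor status at any pre assessment, test the predicted percentage adopting against 0. The candidate predictors listed for the propensity score do not include survey history. No first-survey analysis is described.

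**The concern.** The questionnaire asks whether the student is a designated donor and whether they have discussed the choice with family. Knowledge and attitude scores are analysed as well. Being asked such questions can itself prompt the behaviour or the learning. If it does, students surveyed before would answer differently at a later assessment even with no intervention.

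Nothing in the described models would remove this. The assessment indicators carry the pre/post contrast itself and describe campus and time, not a student's own history. Handling of repeated measures corrects standard errors but not a shift in the mean. Recruiting separately for surveys and contests does not stop the survey from acting as a prompt. At stake is whether a pre-to-post gain can be attributed to the website and contests rather than partly to the questionnaire.

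**Working it through.** **1. The plan's own figure.** The sample size section gives 240 participants per assessment, 9 pre and 11 post assessments, 60% donors at baseline, two-sided alpha 0.05 and 80% power. It states a minimum detectable difference (MDD) of 4 points overall.

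- Pre: 9 × 240 = 2,160. Post: 11 × 240 = 2,640. Total 4,800.
- Two-proportion test, pooled variance, 60% against 64%: power 81.1%. Solving for 80% power gives an MDD of 3.9 points.
- A t-test on 9 against 11 unadjusted assessment proportions (20,000 simulations) gives 76.9% power at 4.0 points and 80.5% at 4.2.

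The stated 4 points is reproduced.

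**2. Bias in the primary cross-sectional contrast.** Let r_pre and r_post be the shares of respondents surveyed before, and τ the testing effect. Then

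bias = (r_post − r_pre) × τ.

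The documents give neither the shares nor τ, so every value below is an assumption:

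| Excess share in post | τ = 2 points | τ = 5 points | τ = 10 points |
|---|---|---|---|
| 0 | 0 | 0 | 0 |
| 10 points | 0.2 | 0.5 | 1.0 |
| 20 points | 0.4 | 1.0 | 2.0 |
| 30 points | 0.6 | 1.5 | 3.0 |

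**3. Is an excess plausible?** If each of the three campuses began with a pre assessment (Figure 1 is not shown, so this is assumed), 3 of the 9 pre assessments contain no repeat takers. With equal assessment sizes and a constant repeat share r afterwards, r_pre = (6/9)r and the excess is r/3. For an assumed r of 30%, that is 10 points. Student turnover could reduce it to zero or below.

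**4. Consequence for the test.** With no true effect, the standard error is √[0.24 × (1/2,160 + 1/2,640)] = 1.42 points. A bias of 0.5, 1.0 or 1.5 points raises two-sided rejection from 5% to about 6%, 11% or 18%. The t-test on 20 proportions gives about 6%, 10% and 17%.

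**5. Longitudinal and adoption analyses.** Every student in the longitudinal set has at least one baseline survey, so each post record comes from someone already surveyed, whereas each student's first pre record does not. In the first pre-to-post change, r_post − r_pre is therefore 1, and the whole of τ is mixed with the intervention. The adoption test against 0 has no untreated comparison, so adoption prompted by the survey counts in full.

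**6. Precision of the sensitivity analyses.** Surveys are treated as independent and repeat shares are assumed. First-survey sizes are 2,160 × (1 − r_pre) and 2,640 × (1 − r_post). For the covariate, the variance inflates by 1/(1 − φ²), where φ is the correlation between being a repeat taker and being in a post assessment.

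| Repeat share pre / post | First surveys, pre / post | MDD, first surveys only | MDD, covariate added |
|---|---|---|---|
| 10% / 20% | 1,944 / 2,112 | 4.3 | 4.0 |
| 10% / 30% | 1,944 / 1,848 | 4.4 | 4.1 |
| 10% / 40% | 1,944 / 1,584 | 4.6 | 4.2 |
| 20% / 50% | 1,728 / 1,320 | 5.0 | 4.1 |

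The comparator is 3.9 points from step 1.

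**The case against.** The strongest reply is that nothing in the documents shows a testing effect, and that the primary contrast may be hardly affected. Students could complete several pre surveys, so repeat takers fall on both sides and only an excess in post matters. The documented email re-invitation is opt-in and confined to the same semester. Where both surveys of a semester fall in the same phase, it adds repeat takers within that phase. The survey sequence is laid out in Figure 1 and accrual in Figure 2, neither of which is available here. The 4-point MDD concerns donor status, which may respond less to a questionnaire than family talk or knowledge does: the contest description ties the pledge to the next licence renewal, although the donor registry also counts towards the outcome.

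All of this stands, and it limits the point to a conditional one. It does not show that survey history is handled anywhere, and it does not reach the longitudinal analyses, where the confounding follows from how the set is defined.

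A further objection concerns repair. Predicting at zero earlier surveys in the longitudinal set would be extrapolation, since no post record there has zero. The change from first to second pre survey mixes testing with time drift, for which the power simulation allows 3 points, and with self-selection. In the adoption models that change is zero by construction. This also stands, and it rules out those remedies.

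**Conclusion.** The plan has no means of separating a testing effect from the intervention effect. For the primary cross-sectional contrast the resulting bias is conditional: zero if repeat shares are equal or if no testing effect exists, and 0.5 to 1.5 points for an assumed excess of 10 to 30 points with an assumed testing effect of 5 points. That is modest beside the 4-point MDD but not negligible. For the longitudinal change and the adoption test against 0, the confounding is built in, although its size is equally unknown.

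A reader might infer that the survey did raise donor status or family talk and that the primary result is inflated. The documents do not support this: they report neither a testing effect nor the repeat shares. A reader might also infer that repeated baselines let the plan estimate and subtract the effect throughout. They give an indication before the intervention, but not a correction for the longitudinal or adoption analyses.

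**What to change.** Keep the primary model as described, and add the following using the email identifiers already held:

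- Report the share of previously surveyed students at each of the 20 assessments. This alone shows whether an excess in post exists.
- Repeat the primary pre/post contrast for donor status, family talk, knowledge and attitudes on each student's first survey only. This removes any carry-over from earlier study surveys in the cross-sectional contrast.
- As a second sensitivity analysis, add the number of earlier surveys as a covariate to the cross-sectional models.
- Compare first-time and repeat takers within the same pre-intervention assessment, as a descriptive indication of a testing effect. Note that it also reflects who chooses to repeat.
- In the longitudinal and adoption analyses, do not predict at zero earlier surveys. State that change from baseline cannot be attributed to the intervention apart from the survey.

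The cost is one derived variable, some reruns and some precision: the MDD rises to about 4.3 to 5.0 points for first surveys only and 4.0 to 4.2 with the covariate, under the assumed repeat shares. First-time takers late in the study may also differ from those early on, so a gap between the first-survey and primary results would not by itself prove a testing effect. Survey recruitment ended in December 2016, so all of these should be labelled post-hoc sensitivity analyses.

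### Family talk has no stated recall period, so neither its same-student rise nor a never-talked percentage above zero shows an effect on its own

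*Combined protocol and SAP*

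**What the plan says.** The list under Survey questions for primary outcomes describes the second outcome in words that begin "Reported discussion about their choice to be (or not be) an organ donor on their DMV issued"; the other party to the talk is a parent or another relative. The primary hypothesis, in section 4 (Statistical Analyses Protocols), refers to students "who spoke to their parents about their choice to be (or not be) a DOD on their license". Neither place says over what period the talk is counted, or ties it to the intervention period.

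The primary analysis is cross-sectional. It is a logistic model on indicators for the 20 assessment points, "adjusted for student's age, sex, race, and religion", after which "the predicted statuses were compared between pre-intervention and post-intervention assessments using a t-test to test the primary hypothesis".

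Two further analyses use students with at least one pre-intervention and at least one post-intervention survey:

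- "The primary analysis models were repeated in the longitudinal sample, accounting for repeated measures".
- For donor status, students with no pre-intervention yes are modelled at post-test, and the predicted percentage adopting is compared with zero by a t-test. A similar analysis is specified for family talk "in the subset who never reported having this conversation on any pre-intervention survey".

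The power section gives a baseline rate and a minimum detectable difference for donor status only. Its allowance for pre-intervention drift also concerns donor status. It has no figure for family talk.

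**The concern.** The intervention aims to prompt new conversations. Table 1 lists a contest theme about telling one's mother and other family in all four intervention semesters. An outcome without a time limit cannot separate those conversations from earlier ones.

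If the item asks about any past discussion, a truthful and consistent student who answers twice has two possible paths: stay the same, or change from no to yes. Some students will have a first talk in any given semester for unrelated reasons. In the longitudinal sample each such talk adds to the post percentage, so a rise is expected even if the contests do nothing. Accounting for repeated measures corrects the standard error but not this drift. In the never-talked subset, zero is the wrong no-effect value whenever background talks occur at all.

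At stake is whether the longitudinal family-talk results can be read as support for the intervention on one of its two primary outcomes.

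**Working it through.** **1. The plan's own figure.** The only stated benchmark is a detectable difference of 4 points overall, for donor status. The inputs from the power section are 240 surveys per assessment, 9 pre and 11 post assessments, 60% at baseline, two-sided alpha 0.05 and 80% power. Surveys are treated as independent, which approximates the plan's simulation.

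- n1 = 9 × 240 = 2,160; n2 = 11 × 240 = 2,640.
- Pooled proportion for 60% against 64%: (2,160 × 0.60 + 2,640 × 0.64) / 4,800 = 0.622.
- SE under the null: √[0.622 × 0.378 × (1/2,160 + 1/2,640)] = 0.01407.
- SE under the alternative: √[0.60 × 0.40/2,160 + 0.64 × 0.36/2,640] = 0.01409.
- Power = Φ[(0.04 − 1.96 × 0.01407) / 0.01409] = Φ(0.88) = 81.1%.

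The difference detectable at 80% power is about 3.95 points, so the stated 4 points reproduces. It applies to donor status in the full cross-sectional data, not to family talk or to the longitudinal subset.

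**2. Same-student rise with no effect, if the item is a lifetime one.** Let p be the share who have already talked at pre, h the share of the rest who first talk in a semester, and k the number of semesters between surveys. With accurate answers:

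rise = (1 − p) × [1 − (1 − h)^k]

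The documents give none of these inputs, so all are assumptions.

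| p | h | k | rise (points) |
|---|---|---|---|
| 60% | 5% | 1 | 0.40 × 0.05 = 2.0 |
| 40% | 10% | 1 | 0.60 × 0.10 = 6.0 |
| 60% | 5% | 2 | 0.40 × (1 − 0.95²) = 3.9 |
| 40% | 10% | 2 | 0.60 × (1 − 0.90²) = 11.4 |

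A wider range (p 30–60%, h 2–10%, one or two semesters) runs from 0.40 × 0.02 = 0.8 to 0.70 × 0.19 = 13.3 points.

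**3. Never-talked subset with no effect.** The expected percentage is 1 − (1 − h)^k. Over the wider range it runs from 2% (h = 2%, k = 1) to 1 − 0.90² = 19%. In an assumed 200 students, the chance of at least one new yes is 1 − 0.98^200 = 98% even at the lowest rate.

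Recall error adds to this. Suppose p = 50%, h = 5%, one semester, and 95% of past talks are reported at each survey:

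- Students with no reported pre-intervention talk: 1 − 0.50 × 0.95 = 52.5% of the sample.
- Share of these who had in fact talked: 0.025 / 0.525 = 4.8%.
- Share of these reporting yes at post-test: 0.95 × (0.025 + 0.025) / 0.525 = 9.0%, against 5% with perfect recall.

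**4. The cross-sectional primary test.** Respondents differ between assessments, so the percentage can fall. A lifetime item counts earlier talks at both pre and post. A prompted talk registers only in a student who had not talked before. If prompted talks were equally likely in both groups and 40–60% had already talked, only 60–40% of them would show. The main consequence there is dilution. Age adjustment may absorb part of any drift.

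**The case against.** The strongest reply is that the item's wording is not visible. A figure marker stands directly under the survey-question heading, and the two lines below it read as outcome descriptions rather than questionnaire text, so a recall period may have been in what was removed. Nor does the phrase "in the subset who never reported having this conversation on any pre-intervention survey" settle the matter. It sorts students by their answers across surveys and would fit a windowed item too, and the plan uses the same construction for donor status, which is a reversible state. This stands: the lifetime reading is an inference, and the point has to be conditional on it.

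Second, the primary test is the age-adjusted cross-sectional comparison, not the same-student one. This also stands. A reader might infer that family talk can only rise in the primary analysis. The documents do not support that, because the sample changes between assessments. Even in repeat responders, inconsistent answers allow a change from yes to no.

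Third, background accumulation is not peculiar to a missing window, since students also become donors over time without an intervention. That is true, but it does not rescue the longitudinal family-talk analyses. It means that the null value of zero needs the same scrutiny for donor status.

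Fourth, all the rates in the illustration are assumed, and the 4-point figure belongs to a different outcome and data set. Both are correct. The arithmetic shows that the drift need not be trivial. It does not show its actual size or a false-positive rate.

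**Conclusion.** The point holds for the two longitudinal family-talk analyses, on condition that the item asks about any past discussion. In that case a positive same-student change, and a never-talked percentage above zero, are both expected without any intervention effect. The size cannot be taken from the documents. Illustratively it is 2–6 points after one semester and 3.9–11.4 after two, if 40–60% have already talked and 5–10% of the rest first talk in each semester.

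Three stronger conclusions are tempting but not supported:

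- That the plan defines the outcome as ever having talked. No section says so.
- That the primary cross-sectional test has a built-in positive sign. Its main exposure is dilution of a true effect.
- That the drift exceeds what the study can detect. The 4-point figure is for donor status in the cross-sectional data and is no threshold for this analysis.

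**What to change.** In the longitudinal paragraphs of the Statistical Analyses Protocols, state that neither the pre/post rise in family talk nor a never-talked percentage above zero will be taken on its own as evidence of effect. Compare each with the background first-talk rate, estimated from students with two or more pre-intervention surveys who answered no at the first. The plan allows more than one pre-intervention survey per student but does not say how many students have them. The intervals between surveys should be comparable, or the rate expressed per semester. If the rate cannot be estimated, report both results as descriptive. State the exact item and its recall period with the results.

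Survey recruitment ended in December 2016, so the item cannot be reworded here. A fixed-window question is an option for a future study, not a replacement primary outcome for this one. It has costs of its own: end-of-semester surveys and the start-of-semester surveys that follow could cover the same window, talks during breaks could be missed, and a student prompted in one semester would revert to no later.

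The change needs no new data, only analysis and wording. The price is a longitudinal family-talk result that is less favourable and less precise.
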